4.5.1 Early Termination Study Visit

Subjects who withdraw from the study will have all procedures enumerated for Visit 16 at the early termination visit.

5 STUDY EVALUATIONS AND MEASUREMENTS

5.1 Screening and Monitoring Evaluations and Measurements

5.1.1 Medical Record Review

Child demographic information

- o Age
- o Sex
- o Race
- o Ethnicity
- o BMI
- Current medications
- o Current diagnoses
- o Zip code
- Contact information
- o CHOP site where child receives primary care services

5.1.2 Other Evaluations, Measures

- Measures at baseline:
 - Caregiver/family Demographic Questionnaire: Caregivers will complete a
 caregiver and family demographic questionnaire. Caregiver/family data will
 include age, sex, race, ethnicity, highest educational level obtained,
 relationship to child, income, employment status, marital status, current
 public assistance, number of times the family has moved in the last year, and
 number of children and adults living in the home.
 - o *Brief Child Sleep Questionnaire (BCSQ):* Caregivers will complete the 30-item BCSQ^{28, 29} to report on child sleep habits (sleep time, day/night sleep duration, night wakings, aspects of the sleep environment, etc.) and the severity of any caregiver-perceived sleep problems. The BCSQ is appropriate for children ages 2-5 years and has shown good reliability and moderate correspondence with actigraphic recordings of child-sleep.^{28, 29}
 - Child Sleep Hygiene Questions: Caregivers will report on child caffeine consumption, electronics in the bedroom, and noise in three questions drawn from our previous research.²³
 - o *Child Behavior Checklist (CBCL):* Caregivers will complete the 99-item Achenbach System of Empirically Based Assessment CBCL for children ages 1.5 to 5 years to report on child internalizing, externalizing, and attention problems.³⁰ The CBCL has shown strong reliability and validity in large validation studies and is a widely used measure of child behavior.³⁰
 - Center for Epidemiological Studies Depression Scale-Revised (CES-D-R):
 Caregivers will report on their own depressed mood using the 10-item CES-D-R short form.³¹⁻³³ This indicator will be used as a control variable in study analyses. The CES-D-R has shown good reliability and validity in diverse adult samples.³¹⁻³³

- Connor-Davidson Resilience Scale 10 (CS-RISC-10): Caregivers will complete the 10-item CS-RISC-10 scale^{34, 35} to report on resilience, which may buffer the impact of child sleep concerns on caregiver mood. This indicator will be used as a control variable in study analyses. The CS-RISC-10 has shown good psychometric properties in community samples.³⁵
- Confusion, Hubbub, and Order Scale (CHAOS): Caregivers will complete the 15-item CHAOS scale³⁶ to report on family organization and routines. This indicator will be used as a control variable in study analyses. The CHAOS scale has shown good psychometric properties in a diverse sample.³⁶

• Measures during 14-day intervention period:

- Objective child sleep will be assessed using a Philips Respironics, Inc., Actiwatch Spectrum,³⁷ which is a water-resistant accelerometer device. Consistent with guidelines for the reliable and valid use of actigraph devices in children,^{38, 39} caregivers will be instructed to keep the actigraph on their child's ankle continuously for the 14-day study period, with the exception of bath time or swimming, to ensure that at least 10 days of data (to account for 4 days of missing data) are obtained.^{38, 39} Caregivers will be asked to press an event marker at lights-off and lights-on. Actigraph data show an 85.1-88.6% agreement with polysomnography, which is the gold standard for objectively assessing sleep.^{38, 39} Actigraph data will be analyzed using Philips Actiwatch software³⁷ and scored using guidelines for young children.³⁷ Actigraphs will generate daily total estimates of child nighttime sleep duration, bedtime, bedtime variability, sleep onset latency, and night wakings.
- O Sleep Diary and sleep location: Child sleep each night will be assessed via a diary as part of standard procedures for actigraphy validation.^{38, 39} Fourteen questions related to child bedtime, wake time, sleep onset latency, night wakings, caregiver perception of child sleep quality, and child sleep location will be drawn from the BCSQ.^{28, 29}
- Daily caregiver-reported child behavior: Caregivers will report on daily child behavior using 5 items adapted from the CBCL and Brief Problem Monitor⁴⁰,
- Daily self-reported caregiver mood and sleep: Caregiver mood will be assessed using 3 items adapted from the Positive and Negative Affect Scale,⁴² which has shown good reliability and validity in diverse adult samples.^{42, 43} Caregiver sleep will be assessed using one item as assessed using one item drawn from the Pittsburgh Sleep Quality Index,⁴⁴ which has shown good psychometric properties.^{44,45}

• Measures at 1-month follow-up:

- o *Brief Child Sleep Questionnaire (BCSQ):* Please see above for the BCSQ^{28, 29} information.
- Child Behavior Checklist (CBCL): Please see above for CBCL³⁰ information.
- o Semi-Structured qualitative interview: Please see the attached semi-structured interview protocol, which contains questions related to caregivers'

perceptions about sleep health and common behavioral sleep treatment approaches.

5.2 Efficacy Evaluations

5.2.1 Diagnostic Tests, Scales, Measures, etc.

The primary objective of this study is to evaluate the impact of provision of a child bed through the Beds for Kids program on objectively measured child sleep, and on daily child behavioral functioning, caregiver mood, and caregiver sleep over 14 days for preschool-aged children. The following measures will be used to determine the impact of bed prevision through the Beds for Kids program on child sleep, daily child behavior, and daily caregiver mood and sleep:

- Actigraph
- Caregiver-reported child sleep diary
- Caregiver-reported daily child behavior ratings
- Caregiver self-reported daily mood and sleep ratings

The first two of the secondary study objectives are to determine the impact of poor child sleep on daily child behavior, caregiver mood, and caregiver sleep, and to determine the impact of bed provision on child sleep at one-month follow-up. The following measures will be used for these objectives:

- Caregiver-reported child sleep at baseline and one-month follow-up
- Actigraph
- Caregiver-reported child sleep diary
- Caregiver-reported daily child behavior ratings
- Caregiver self-reported daily mood and sleep ratings

The final secondary study objective is to identify caregivers' perceptions of barriers and facilitators related to sleep health and common behavioral sleep treatment approaches (one-month post-bed delivery). The following measures will be used:

• Caregiver-reported qualitative interview

5.3 Pharmacokinetic Evaluation

Not applicable.

5.4 Safety Evaluation

Participant safety will be monitored by adverse events and examination of all validated child behavior (CBCL) and caregiver mood (CES-D-R) rating scales. Lead Investigator [name] will review all questionnaires completed by families within 3 business days of completion in order to screen for clinically significant child behavior or caregiver mood concerns. In the event of clinically significant concerns Lead Investigator [name] will contact the family by phone within 3 business days using the EMR for family contact information, to provide the family with appropriate community referrals for behavioral health services, as well as the information of the CHOP social workers employed at the primary care sites from which families are referred. For clinically significant ratings of caregiver depressed mood, [name] will also further assess the caregiver for any safety risks (suicidal or homicidal ideation, plan, or intent). Should there be an imminent risk caregiver safety, we will contact emergency services (911 or Pennsylvania mobile crisis services) for further suicide/homicide/risk assessment. In the rare event that a participant necessitates psychological treatment due to adverse effects of study participation while completing study measures, the trained research assistant will contact [name] by phone, and [name] will speak with the participant, provide behavioral health resources, and screen for caregiver suicide/homicide risk in the manner described above. Although we are not asking caregivers to report on any instances of child abuse or neglect, should a caregiver spontaneously disclose this information to us during the study procedures or risk assessment we will file a Department of Human Services report in this regard, consistent with mandated reporting standards. All information obtained during the risk assessment will be used only for the purposes of determining appropriate follow-up care. Information about child-related safety screening and mandated reporting will be documented as a telephone encounter in the child's medical record, and will not be stored with study data, or used for any study-related data analysis. It will not be stated in the medical record documentation that the child or caregiver are participating in a research study. For caregiver risk assessment procedures, risk assessment will be documented in a Note to File coded by the participant ID and will be stored separately from the consent form and in a separate REDCap database used for tracking purposes only. Investigator and Licensed Psychologist [name] and the Lead Investigator and Psychology Postdoctoral Fellow [name] will meet weekly to monitor safety and will be in contact by phone during all data collection periods.

6 STATISTICAL CONSIDERATIONS

6.1 Primary Endpoint

The primary endpoint is the change in objective and caregiver-reported child sleep.

6.2 Secondary Endpoints

Secondary endpoints will include the following:

- The association between child sleep and next-day child behavior (Aim 2)
- The association between child sleep and next-day caregiver mood (Aim 2)

- The association between child sleep and caregiver sleep (Aim 2)
- The change in child sleep based on caregiver report at baseline and one-month follow-up (Aim 3)

6.3 Statistical Methods

6.3.1 Baseline Data

Data for the primary objective and first two secondary objectives will be analyzed using Mplus Version 8.⁴⁶ Data will be summarized using descriptive statistics (means and percentages). We will examine the normality of the data and adjust analyses as needed.

6.3.2 Efficacy Analysis

The primary analysis will be based on an intention to treat approach and will include all randomized subjects. To evaluate the impact of provision of a child bed through the Beds for Kids program on child sleep (Hypothesis 1a), we will compare children in the study condition who received a bed at day 7 to those in the waitlist control condition (bed at day 14) on objectively and subjectively measured sleep variables using two-level multilevel mixed models. Multilevel models allow for an examination of both within-child (daily assessments, level 1) and between-child (level 2) associations between sleep and daily child and/or caregiver functioning.²⁰ Child age, sex, baseline caregiver mood and resilience, and family chaos as level 2 covariates, given research showing that these variables impact child sleep. ^{7, 9, 12} To examine whether children who receive a bed at day 7 show improved behavior, increased caregiver mood, and better caregiver sleep relative to children in the waitlist condition (Hypothesis 1b), we will run three different multilevel mixed effect models, using child daily behavior, caregiver mood, and caregiver sleep scores as the outcomes, respectively. Analyses will include child sleep location, age, sex, baseline caregiver mood and resilience, baseline family chaos, and baseline child internalizing and externalizing behavior at model level 2 as covariates.

Aim 2: To determine the impact of poor child sleep (short sleep duration, later bedtimes, inconsistent bedtimes, night wakings, and poor sleep quality) on daily child behavior and caregiver functioning (mood and sleep) (Hypothesis 2a), we will specify two-level multilevel models. We will use data from week 1 of the study, as at that time children in both conditions will not have received a bed through the Beds for Kids program. We will also specify models using 2-week data from those in the intervention group to assess whether improved sleep after week 1 as a result of receiving a bed also leads to improved functioning. In these models, each child sleep variable is entered as a predictor of each of the functional outcomes at level 1. Child behavior, caregiver mood, and caregiver sleep variables will be specified as outcomes in separate models. Covariates (as described for Aim 1) will be added to level 2. This multi-level modeling approach is consistent with other studies assessing associations between sleep and next-day child functioning.²⁰ To test whether the effects of poor sleep are cumulative (Hypothesis 2b), with children with poor sleep across multiple nights exhibiting the worst behavior, lowest caregiver mood scores, and worst caregiver sleep, we will run separate two-level multilevel models by outcome with averaged (cumulative) child sleep variables across week 1 nights as the predictors of

average child behavior, caregiver mood, and caregiver sleep ratings across this period. Child age, sex, baseline behavior, baseline family chaos, and baseline caregiver mood and resilience will be entered as level 2 covariates.

Aim 3: To determine whether provision of a child bed is associated with improved sleep health (longer nighttime sleep, earlier bedtimes, more consistent bedtimes, decreased night wakings, and better sleep quality) from baseline to one-month follow-up across study conditions (Hypothesis 3a), we will regress each follow-up sleep outcome on the baseline sleep outcome, with covariates including child age, child sex, study condition (to control for amount of time child has had the bed), and baseline caregiver mood and resilience, family chaos, and child behavior.

Aim 4: To identify caregivers' perceptions of barriers and facilitators related to sleep health and common behavioral sleep treatment approaches, we will use grounded theory approach that allows for relevant themes to emerge from the transcribed interview data. We will create a codebook using the first three interview transcripts to identify relevant themes. Once a stable codebook has been established, all transcripts will be coded using OSR NVivo[©] or ATLAS software. Once the coding is complete, we will examine each code to identify patterns in the data and key themes. We will integrate coded interview data with the quantitative study data above (i.e., caregivers' report of child sleep patterns and problems; actigraphy-derived data) to identify how barriers and facilitators may vary by child sleep habits.

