This is a randomized controlled trial (RCT). Caregiver-child dyads will be assigned to the intervention group, in which they receive a bed through the Beds for Kids program after a 7-day period, or to the waitlist control group, in which they receive a bed after a 14-day period.

Setting/Participants:

This is a single site study to be performed at CHOP. A total of 50 caregiver-child dyads (child age 2 to 5 years) will be recruited from clinicians at CHOP primary care sites. Families must be eligible for the Beds for Kids program: (a) child is living without his/her own bed and (b) family is at or below 100 percent of the Federal Poverty Guideline.

Study Interventions and Measures:

Caregivers in the intervention and waitlist control conditions will complete measures of child sleep and behavior, as well as caregiver functioning (mood; resilience; sleep) and family functioning (i.e., chaos). Over a 14-day period, children in both study conditions will wear actigraphs to objectively measure sleep, and caregivers will complete daily ratings of child behavior, caregiver mood, and caregiver sleep. At one-month after bed delivery, caregivers will complete measures of child sleep and behavior. At one-month follow-up,

[figure not shown]
caregivers will also be given the option to participate in a brief, semi-structured qualitative interview related to barriers to and facilitators of sleep health and behavioral sleep treatment.

The primary study outcome is the difference between study conditions in actigraph-derived and caregiver-reported child sleep (bedtime, bedtime variability, sleep quality, night wakings, total sleep duration) for days 7 to 14 (bed vs control), as well as compared to baseline. Thus, this is a mixed between (bed vs waitlist) and within (days 1-7 vs days 8-14) group design.

TABLE 1: SCHEDULE OF STUDY PROCEDURES

Study Phase	Screening															One month Follow-up	
Visit Number	0	1	2	3	4	5	6	7	8	9	10	11	12	13	14	15	16
Approximate Study Days (May vary by 7 days)	0	1	2	3	4	5	6	7	8	9	10	11	12	13	14	15	36-43 (dependent on bed delivery date)
Chart review	X																
Verbal Informed Consent	X																
Review Inclusion/Exclusion Criteria	X																
Randomization	X																
Caregiver-reported caregiver and family demographic information		X															
Caregiver-reported child sleep and behavioral measures, caregiver resilience, mood, and family chaos measures		X															X

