Medical record review and child demographic data abstraction		X															
Actigraphy (objective sleep measurement)			X	X	X	X	X	X	X	X	X	X	X	X	X	X	
Caregiver-reported daily questionnaire (caregiver and child sleep and mood)			X	X	X	X	X	X	X	X	X	X	X	X	X	X	
Bed provision (day 7 for intervention group; day 14 for waitlist control group)									X							X	
Caregiver semi-structured interview about barriers to and facilitators of sleep health and behavioral sleep treatment																	X
Adverse Event Assessment	X	X	X	X	X	X	X	X	X	X	X	X	X	X	X	X	X

FIGURE 1: STUDY DIAGRAM

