6.4 Sample Size and Power

Based on power analysis²⁶ and a recent study of youth sleep and daily mood,²⁰ which detected a medium effect of nighttime sleep on daily mood, a total of 25 participants are needed across 14 days to detect medium (.35 to .45) daily effects of sleep on mood with 80% power and a p-value of <.05. To compare the two study groups (7-day and waitlist control) on the effects of Beds for Kids, 24 subjects (12 per group) are needed to detect an effect size of .45 with 80% power and a p-value of <.05, using repeated measures analysis of variance, 14 measures per subject, and a correlation of 0.5 among repeated measures. Our proposed sample of 50 caregiver-child dyads is thus sufficient, and will accommodate analyses for Aims 2 and 3.

A total of 5-10 qualitative interviews are needed to accommodate analyses for Aim 4. This sample size was based on semi-structured interview guidelines for qualitative research.⁴⁷

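### The Hypothesis 1b models adjust for child sleep location without a time point; a value that includes nights after bed delivery would remove part of the bed effect from a between-child arm comparison

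*Combined protocol and SAP*

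**What the plan says.** For Hypothesis 1b, section 6.3.2 states: "we will run three different multilevel mixed effect models, using child daily behavior, caregiver mood, and caregiver sleep scores as the outcomes, respectively". The covariate sentence follows: "Analyses will include child sleep location, age, sex, baseline caregiver mood and resilience, baseline family chaos, and baseline child internalizing and externalizing behavior", all at level 2, which the same section defines as the between-child level. Caregiver mood and resilience, family chaos and child behavior are marked as baseline in that sentence. Sleep location is the only changeable covariate there that is not.

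Section 5.1.2 names sleep location once, in the nightly diary listed under the 14-day intervention period: "Fourteen questions related to child bedtime, wake time, sleep onset latency, night wakings, caregiver perception of child sleep quality, and child sleep location". The diary items are drawn from the BCSQ, which caregivers also complete at Visit 1. There it is described as covering aspects of the sleep environment, without naming location.

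Table 1 runs the daily questionnaire across the whole 14-day measurement period and gives the delivery times as "Bed provision (day 7 for intervention group; day 14 for waitlist control group". Section 3.4.1 requires that children have no individual bedding at entry.

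On the contrast, the Abstract says "Thus, this is a mixed between (bed vs waitlist) and within (days 1-7 vs days 8-14) group design". It also describes a comparison of the conditions over days 7 to 14, stated there for child sleep. Section 6.3.2 does not say which model term carries the bed effect for Hypothesis 1b.

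**The concern.** Where a child sleeps after day 7 is what the intervention is meant to change. If the level 2 value is built from diary nights that include days after delivery, it is measured after randomization and is partly caused by assignment. A between-child arm term adjusted for it no longer estimates the total effect of receiving the bed. It estimates only what is left after the route through location is held fixed. It is also less precise, because location and arm become strongly correlated. Any common cause of own-bed use and outcome could then bias it in either direction.

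At stake are the three Hypothesis 1b outcomes, which sit under the primary objective in section 2.1. A real benefit to behavior, caregiver mood or caregiver sleep could be reported as smaller than it is, or missed. Because the time point is open, the choice could also be made after the data are seen.

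**Working it through.** **1. Where the text leads.** Harm needs two conditions.

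- *The value includes post-delivery nights.* Section 5.1.2 names only the nightly diary as a source. No section gives a rule for turning nightly values into one child-level value, and none says the Visit 1 BCSQ is the source. Both readings are open.
- *The bed effect is read from a between-child arm term.* The Abstract's days 7 to 14 comparison is such a contrast. Its mixed design also allows arm by period. Both readings are open.

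**2. The plan's own sample size.** Section 6.4 says "24 subjects (12 per group) are needed to detect an effect size of .45 with 80% power", "using repeated measures analysis of variance, 14 measures per subject, and a correlation of 0.5 among repeated measures". Reading .45 as Cohen's f, with N subjects, m measures and correlation rho:

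- Between groups: lambda = f² × N × m / (1 + (m − 1) × rho) = 0.2025 × 24 × 14 / 7.5 = 9.07, with 1 and 22 degrees of freedom. Power is 0.821; N = 22 gives 0.783. The stated 24 is reproduced.
- Interaction: lambda = f² × N × m / (1 − rho). With m = 14, N = 4 gives 0.729 and N = 6 gives 0.960. With m = 2, N = 10 gives 0.704 and N = 12 gives 0.802. Neither leads to 24.

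So 6.4 was sized on a between-subject term. That makes the between-child reading realistic, but it does not settle what 6.3.2 will fit.

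**3. Illustrative size for an arm term on the post-bed nights.** Taken from the documents: 50 dyads at 1:1, treated as 25 per arm; 7 nights; correlation 0.5. Assumed, not in the documents: an effect of 0.90 SD (2 × .45) on those nights, own-bed use of 70% versus 5%, location coded as user or non-user, and the share of the effect acting through location.

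- Variance of a child's 7-night mean: 0.5 + 0.5/7 = 0.571. Standard error of the arm difference: sqrt(0.571 × 2/25) = 0.214.
- Share of location variance explained by arm: 0.25 × 0.65² / (0.375 × 0.625) = 0.451. Variance inflation: 1/(1 − 0.451) = 1.82. Standard error with location: 0.214 × sqrt(1.82) = 0.288.
- Expected estimate with location: 0.90 × (1 − mediated share).

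Simulation (4,000 replicates per setting) agrees:

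| Mediated share | Estimate without location | Estimate with location | Rejection without | Rejection with |
|---|---|---|---|---|
| 0% | 0.90 | 0.90 | 98% | 85% |
| 25% | 0.90 | 0.67 | 98% | 60% |
| 50% | 0.90 | 0.46 | 97% | 33% |
| 75% | 0.90 | 0.22 | 96% | 11% |
| 100% | 0.90 | 0.00 | 92% | 5% |

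The first row shows the precision loss alone. With own-bed use of 50% or 90% instead of 70%, the estimates stay within 0.01, and rejection with location at 50% mediation is 43% or 19%. With no mediation but an assumed common cause (1 log-odds of own-bed use and ±0.4 SD of outcome per SD), the adjusted arm term is 0.69 or 1.11 instead of 0.90, by sign.

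**4. Cases without harm.**

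- *Baseline or week 1 location.* In a separate simulation with other codings of location, the estimate stays at about 0.90 and power at about 0.95 to 0.99, as with no location covariate.
- *Arm by period, location as a main effect.* A value that is constant within a child cancels in the week 2 minus week 1 difference. In complete simulated data the contrast is 0.903 with and without location at 50% mediation. With 4 of 14 nights lost at random, the largest change in any one simulated trial is 0.008.

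**The case against.** The text can fairly be read as harmless. Section 6.3.2 ties level 1 to daily assessments and puts location at level 2, among fixed or baseline traits. Where the plan averages nightly data (Hypothesis 2b) it says so, and it says nothing of the kind for location. Baseline location varies (floor, sofa, crowded bed), so a Visit 1 value would be a meaningful covariate. The missing label is weak evidence of intent, because family chaos also lacks it in the Hypothesis 1a list. All of this stands as support for a baseline reading. It does not exclude the other one: a mean over diary nights is also a between-child value, and the diary is the only named source.

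Three stronger inferences are tempting, and the documents do not support them.

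- *That the plan breaks its intention-to-treat commitment.* The sentence reads "The primary analysis will be based on an intention to treat approach and will include all randomized subjects". It concerns the primary analysis and who is included. The primary endpoint in 6.1 is child sleep, and the Hypothesis 1a covariates omit location. The objection to adjusting for a post-randomization variable has to stand on its own, and it does.
- *That section 6.4 proves the bed effect is the arm term.* It names repeated measures analysis of variance rather than the multilevel models of 6.3.2, and it treats all 14 measures alike although neither arm has a bed in week 1. It looks like a simplified sizing exercise.
- *That the power losses above are what this trial will suffer.* They rest on assumed bed use, mediated share and coding. In 6.4's formula, .45 corresponds to 0.90 SD in the 14-night mean, not on post-bed nights alone.

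**Conclusion.** The point holds as an open specification with a foreseeable bad reading, not as a demonstrated bias. Sleep location has no time point, and its only named measure runs past delivery. If post-delivery nights enter the value and the bed effect is a between-child arm comparison, the estimate loses the part of the effect that acts through location, and precision falls. That direction follows from the entry criteria, the delivery schedule and the model. The size does not: under the assumptions shown, a 0.90 SD effect falls to between 0.67 and 0.00 SD as the mediated share rises from 25% to 100%.

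No harm arises from a pre-delivery value. In complete data none arises from an arm-by-period contrast with location as a main effect only. The reach is the three Hypothesis 1b outcomes; Hypothesis 1a and the primary endpoint are not affected. Severity is minor, and confidence is medium because the intended reading cannot be settled from the text.

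**What to change.** In section 6.3.2, do one of two things:

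- drop child sleep location from the Hypothesis 1b covariates; or
- define it as a pre-delivery value with its coding: the Visit 1 BCSQ response if that form carries the item, otherwise the week 1 diary nights before delivery.

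Use post-delivery location only in a separate analysis labelled as mediation or adherence.

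The cost is one line of text and possibly slightly less covariate information. It needs no new data and no additional families.

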3 INVESTIGATIONAL PLAN

3.1 General Schema of Study Design

3.1.1 Screening and Randomization Phase

Clinicians at the Chestnut Hill, South Philadelphia, Karabots, and Cobbs Creek locations who are already referring families directly to the Beds for Kids program will identify potentially eligible families for this study. Families who are eligible for Beds for Kids will then be asked whether they would be interested in participating in a research study related to the program. The clinician will provide the name, MRN, and contact information of interested families to the study team. The study team will then conduct an initial medical record review to identify whether the referred family is potentially eligible. The study team will then contact the potentially family to initiate informed consent and eligibility screening procedures. Alternatively, families receiving care at any of the CHOP primary care recruitment sites (Chestnut Hill, South Philadelphia, Karabots, or Cobbs Creek) may self-refer to the study if they hear of the Beds for Kids program through word-of-mouth or social

media (e.g., Facebook). However, we will not advertise the study on social media of any kind for recruitment purposes.

The informed consent process will take place by phone, with a member of the study team obtaining verbal consent from the legal guardian for study participation. Child assent will not be obtained as all participating children are under age 5 years. Families will be informed that they are free to decline to participate or to withdraw from the study, and that this will not impact their participation in the Beds for Kids program or any future medical care. After obtaining verbal informed consent, families will be screened for study inclusion and exclusion criteria.

Eligible families will be randomly assigned to receive a bed from Beds for Kids 7 days after initiating the actigraph/daily diary study procedures (intervention condition), or to receive a bed 14 days after initiating these procedures (waitlist control condition). Thus, this is a mixed between (bed vs waitlist) and within (days 0-7 vs days 8-14) group design.

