4.2.1 Visits 1 through 14 (study days 1 through 15 +1-7 days)

Visit 1 (in person):

- Completion of electronic caregiver-reported demographic information
- Completion of electronic caregiver-reported child sleep, child behavior, caregiver resilience, caregiver mood, and family chaos questionnaires
- Provision of incentive for baseline measure completion
- EMR review and data abstraction of child demographic information by a member of the study team.

Visits 2 through 15 (by phone): Visit 2 will occur within 7 days of Visit 1.

- Actigraphy (objective measurement of child sleep)
- Completion of caregiver daily mood and sleep questionnaires by phone

- Completion of caregiver-reported child behavior and sleep questionnaires by phone
- Bed delivery (day 7 after actigraph initiation for intervention condition; day 14 after actigraph initiation for waitlist control condition)
- Provision of incentives for daily measure and actigraph completion
- Scheduling of return of actigraph to study team (during the week following Visit 15)

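### Aim 2's supplementary two-week model uses the intervention arm alone and names no time term, so its sleep-functioning slope can absorb drift in caregiver ratings

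*Combined protocol and SAP*

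**What the plan says.** The main Aim 2 analysis in Section 6.3.2 uses week 1 from both arms, chosen because no child then has a program bed. The section then adds: "We will also specify models using 2-week data from those in the intervention group to assess whether improved sleep after week 1". The rest of that sentence ties the improvement to the bed and gives the question to be answered: "as a result of receiving a bed also leads to improved functioning".

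For the Aim 2 models, "each child sleep variable is entered as a predictor of each of the functional outcomes at level 1", and "Covariates (as described for Aim 1) will be added to level 2". The Aim 1 covariates are age, sex, baseline caregiver mood and resilience and family chaos. Hypothesis 1b adds sleep location and baseline child behavior, also at level 2. No day, week or bed-period term is named for the two-week model.

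On timing, Section 4.2.1 lists: "Bed delivery (day 7 after actigraph initiation for intervention condition; day 14 after actigraph initiation for waitlist control condition". Section 3.1.1 says "this is a mixed between (bed vs waitlist) and within (days 0-7 vs days 8-14) group design". The Abstract says of data collection: "Over a 14-day period, children in both study conditions will wear actigraphs to objectively measure sleep, and caregivers will complete daily ratings". The waitlist arm therefore has the same two weeks of nightly data, with no bed until day 14, but the added model does not use it.

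**The concern.** Level 2 covariates are constant within a child, so none of those listed can absorb change over days. In the intervention arm the bed arrives near the boundary between the weeks. If sleep shifts there, sleep is correlated with calendar time within each child. If caregiver ratings also change over the two weeks for another reason, such as habituation to daily calls, a slope on sleep alone takes up part of that change.

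The bias needs both a sleep shift and rating drift. The analysis presupposes the shift, so drift is the only further ingredient. Drift in the same direction as the sleep improvement creates or inflates a link; drift in the opposite direction masks a real one. The model also carries the most causal wording in Aim 2, so a slope made partly of drift could be reported as benefit from the bed.

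**Working it through.** **The plan's own figures.** Section 6.4 gives 24 subjects for the group comparison and 25 for daily sleep-mood effects.

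- 24: repeated-measures F test with effect .45, 14 measures and correlation 0.5. Noncentrality = 0.45² × 24 × 14 / (1 + 13 × 0.5) = 9.07; power is 82.1% (78.3% at 22).
- 25: reproduced if .35 is read as f² in a one-predictor regression. Noncentrality = 0.35 × 25 = 8.75; power is 80.9%.

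Neither calculation involves a time term, so the point does not alter them.

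**Inputs for the bias.** From the documents: 50 dyads at 1:1 (about 25 per arm), 14 nights, delivery after night 7. Assumed, because the documents give no values: within-child SD of 1 for sleep and ratings, sleep shift s = 0.3 to 0.6, rating drift of 0.2 to 0.4 in total, true slope 0.

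**Spurious slope.** With child-mean centering and 7 nights in each period, let g be the difference in mean rating between the weeks caused by drift:

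bias = 0.25 × s × g / (13/14 + 0.25 × s²)

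For a step, g is the full drift. For linear drift of total D, g = D × 7/13 (0.4 gives 0.215; 0.2 gives 0.108).

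- Linear, smallest case: 0.25 × 0.3 × 0.108 / 0.951 = 0.008
- Linear, largest case: 0.25 × 0.6 × 0.215 / 1.019 = 0.032
- Step, smallest case: 0.25 × 0.3 × 0.2 / 0.951 = 0.016
- Step, largest case: 0.25 × 0.6 × 0.4 / 1.019 = 0.059

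**Type I error.** The standard error is about 1/√(350 × (13/14 + 0.25 × s²)), or 0.053 to 0.055. In the largest linear case, 0.032/0.053 = 0.60, and a two-sided 5% test then rejects about 9.2% of the time. Simulation with 10,000 replicates per cell gave:

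| Sleep shift | Linear drift 0.2 / 0.4 | Step drift 0.2 / 0.4 |
|---|---|---|
| 0.3 | 5.2% / 6.1% | 6.0% / 8.8% |
| 0.45 | 5.5% / 7.0% | 7.3% / 12.8% |
| 0.6 | 5.8% / 9.2% | 9.2% / 19.5% |

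Monte Carlo error is about 0.2 points at 5% and 0.4 at 20%. With no sleep shift, rejection was 4.8% to 5.1%. Spreading delivery over ±6 nights cut the step case to 5.0% to 9.1%. Reversing the drift reverses the sign of the bias and leaves its size unchanged.

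**Both arms plus a week term.** Rejection was 4.7% to 5.5% in all cells with a sleep shift. At s = 0.45 the standard error fell from 0.0544 to 0.0390. Doubling the sample alone would give 0.0544/√2 = 0.0385, so the gain is essentially sample size.

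**Where the slope's information comes from.** As planned, the bed-related shift supplies 0.25s² / (13/14 + 0.25s²) of it: 2.4%, 5.2% and 8.8% at s = 0.3, 0.45 and 0.6. With both arms and a week term, the shift variance left is s²/16, and the share is 0.6%, 1.3% and 2.4%.

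**The case against.** **The plan is silent; it does not exclude a time term.** This stands. Section 6.3.2 is brief, spells out no time terms for the Aim 1 models either, and Section 3.1.1 treats the two periods as a design factor. A reader might infer that the team has ruled out time adjustment; the text does not show that. It does, however, make a definite choice of one arm, and that choice removes the only bed-free estimate of the week 2 trend.

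**A step exactly at night 7 is not natural drift.** Largely right. The only event planned then is bed delivery, and a rating jump caused by the bed would be a direct effect of the bed. Gradual drift is the fairer base case and gives the smaller figures; the step is an upper case. A reader might take 20% as the expected error, but nothing in the documents supports a drift of that form or size.

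**A week term in the intervention arm alone would do.** It does remove the bias (4.5% to 5.4% rejection), but it absorbs the whole average bed-related sleep change. The two-arm model keeps only a small part of that change, so its advantage lies mainly in precision and in a trend estimated partly from bed-free children. It should not be presented as isolating bed-driven improvement.

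**The interpretation is already guarded.** Partly. Section 6.2 defines these endpoints as associations, Hypothesis 2a uses the same language, and Hypothesis 1b tests the bed's effect on functioning against a concurrent control. Only the sentence introducing the two-week model goes further.

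**Conclusion.** The point holds at low severity. Followed as written, the two-week model lets its sleep slope absorb any rating trend that coincides with the bed. Under the assumed values, gradual drift gives about 5% to 10% type I error and a spurious slope of about 0.01 to 0.03 SD per SD of sleep; a step at delivery gives about 6% to 20%. These are illustrations, because the documents supply no drift, sleep shift or SD. Without either a sleep shift or drift, there is no bias.

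A reader might infer that the trial's conclusion about beds is at risk. The documents do not support that: this is a supplementary model for a secondary aim of a self-described pilot. The primary comparison and Hypothesis 1b have a concurrent control. The main Hypothesis 2a model and Hypothesis 2b use week 1 only, so neither spans bed delivery, and the power figures do not depend on this model.

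**What to change.** Fit the two-week model in both arms with a stated week (or day) term, so that the waitlist arm helps supply the time trend. Describe the slope as a time-adjusted association, in line with Section 6.2, and leave the bed's effect on functioning to Hypothesis 1b.

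State two limits. First, the adjusted slope rests almost entirely on night-to-night variation, as the information shares show. Second, families are not blinded (Section 9.1.2), so the bed may affect ratings directly; for direct effects of 0.2 to 0.4 SD without drift, the two-arm model gave 5.0% to 6.8% type I error, against 5.7% to 19.1% for the planned model.

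The cost is one model term, a wider analysis set and a softer sentence. No new data are needed.
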